Myoelectric Activity Following Colorectal Surgery and Return of Bowel Function

Protocol Number

2000032548

Protocol Version

April 21, 2022

1.4

IDE Number:

IDE Holder:

ClinicalTrials.gov Registration: NCT05298774

PRINCIPAL INVESTIGATOR:

Name [name]

Department. Surgery – Division of Colon & Rectal Surgery

[contact]

Email Address [contact]

Confidentiality Statement:

REVISION HISTORY:

Revision #	Version Date

Synopsis

Primary Objective

To measure myoelectric signals with the G-Tech WPS and determine if a correlation exists between signal strength and the rate of gastrointestinal recovery following colorectal surgery. Determine the relationship between gastrointestinal myoelectrical signal strength and clinical markers of recovery such as passage of flatus/bowel movement, oral tolerance of diet, and discharge readiness.

Secondary Objective (if applicable)

To measure myoelectric signals with the G-Tech WPS and determine if there are differences in signal patterns for right colon resections, left colon resections, and rectal resections.

Study Duration

12 months for data collection followed by 12 months of data analysis

Study Design

This is a single-arm, prospective, non-randomized, feasibility study.

Number of Study Sites

1 (Yale New Haven Hospital)

Study Population

Patients undergoing elective colorectal surgery

Number of Participants

200

Primary Outcome Variables

GI functional recovery after surgery as measured by first flatus

Secondary and Exploratory Outcome Variables (if applicable)

Rate of inpatient postoperative ileus; rate of readmission for post-discharge ileus; GI functional recovery as measured by first bowel movement

Abbreviations

Abbreviation	Explanation
AE	Anticipated adverse event
CRF	Case report form
GI	gastrointestinal
SAE	Serious adverse event
WPS	Wireless Patch System

Glossary of Terms

Glossary	Explanation
Erythema	Reddening of the skin that is a non-specific sign of skin irritation, inflammation, or injury. It is caused by dilatation of superficial blood vessels in the skin
Myoelectric	The electric property of a muscle
Rash	A reddened inflamed skin usually temporary
Transcutaneous	Transdermal; performed through the skin

Table of Contents

Preface	Error! Bookmark not defined.
Synopsis	3
Primary Objective	3
Secondary Objective (if applicable)	3
Study Duration.....	3
Study Design.....	3
Number of Study Sites.....	3
Study Population	3
Number of Participants	3
Primary Outcome Variables.....	3

1.1 Introductory Statement

This document is a protocol for a human research study. The purpose of this protocol is to ensure that this study is to be conducted according to ICH GCP guidelines, and according to CFR 21 Part 812, other applicable government regulations, and Institutional research policies and procedures.

2 Background

2.1.1 Device Preclinical Experience

G-Tech Medical has developed a noninvasive wireless patch system that measures electrical activity from the gastrointestinal smooth muscles on the abdominal surface.

2.1.2 Device Clinical Experience

This technology has been studied as part of several non-significant risk IRB approved studies in both adults and pediatric populations to evaluate the patterns of gastrointestinal myoelectrical signals following surgery.²⁰⁻²² The studies demonstrate that signals measured by the G-Tech Wireless patches correlate with clinical markers of postoperative recovery such as time to feeding and time to flatus following pancreaticoduodenectomy and general abdominal surgeries respectively. The study in patients undergoing pancreaticoduodenectomy procedures was conducted in collaboration with researchers at Stanford University.²⁰ The study demonstrated that measurement of gastric activity beginning immediately after pancreaticoduodenectomy with the G-Tech Wireless Patch System, based on the measured spectral peak near 3 cpm, could distinguish patients with shorter or longer times to diet readiness. The study demonstrated the potential utility of the G-Tech Patch System in providing objective data to identify patients who are progressing as well as, or better than expected, and those who are at risk for delayed gastric emptying. In another open, prospective study, researchers examined the use of the G-Tech Wireless Patch System in predicting time to first flatus by looking at colonic myoelectrical activity following general abdominal surgeries.²¹ Patients with early flatus had stronger early colonic activity than patients with late flatus. At 36 h post-surgery, a linear fit of time to flatus vs cumulative colonic myoelectrical activity predicted first flatus as much as 5 days (± 22 h) before occurrence.

2.2 Background/prevalence of research topic

Gastrointestinal recovery after any visceral surgery is a complex dynamic process with multiple factors ranging from complexity of the surgery, degree of bowel handling and preoperative comorbidities affecting whether the recovery happens over few days, or is a slow prolonged affair lasting weeks.¹ Delays in the gastrointestinal recovery process or ileus is accompanied by distention of the abdomen, pain, nausea, vomiting and the inability to tolerate oral feeding.^{2,3} Interventions to alleviate the ileus/distention include insertion or reinsertion of a nasogastric tube, instating *nil per os* and, if necessitated, parenteral

nutrition.⁴ All of these factors contribute not only to patient discomfort, but extend length of stay (LOS), increase hospital resource utilization and thereby add to overall costs.⁵⁻⁷

Clinically, the markers of gastrointestinal recovery are noted by passage of flatus, defecation and the ability to tolerate solid food without significant nausea and vomiting.⁸ Passage of stool or flatus - considered a surrogate for intestinal and anastomotic continuity - is often used as the trigger to start stepwise dietary orders with the patient's ability to tolerate each step marking their readiness for the subsequent meal. Fast-track and Enhanced Recovery After Surgery (ERAS) programs that promote early feeding in advance of these clinical markers, along with opioid sparing techniques and use of minimally invasive procedures have been shown to be safe and beneficial for many patients by demonstrating earlier recovery and shorter length of stay.⁹⁻¹¹ However, it has also been shown that, for as many as 25% of cases, the strategy does not work as noted earlier, with the need for reinsertion of the nasogastric tube and reinstating nil per os status. In a recent study of 513 consecutive colorectal patients who were on an ERAS protocol, 128 patients (24.7%) needed postoperative reinsertion of nasogastric tube at the 3.9 ± 2.9 postoperative day.⁹ This suggests that, while early postoperative feeding is beneficial to patients in whom recovery is on track, it does not work in cases where patients are not ready for it.

At present, there is no reliable measurement that can predict gastrointestinal recovery/diet readiness for patients in advance of these clinical markers that may allow for interventions or fast-track programs to facilitate timely recovery. Auscultation for return of bowel sounds, long part of the standard of care, is controversial in its usefulness to indicate recovery. Bowel sounds have shown to have poor correlation with flatus/defecation and have proved unsuccessful in guiding diet interventions.^{12,13}

Smooth muscle electrical activity on the other hand is directly related to gastrointestinal function and motility. Researchers have previously shown a 1:1 correlation between electrical and mechanical (contractile) events in the colon with internally placed electrode-strain gauge force transducers.¹⁴⁻¹⁶ Electrical activity in the colon has been reported across a wide range of frequencies ranging from 0 to 40 cycles per min (cpm)).¹⁷ Condon et. al have documented the progressive return of colonic electrical activity related to resolution of postoperative ileus and clinical recovery following surgery.^{18,19} These measurements have been performed using electrodes placed internally during surgery, a major impediment towards broader use of such technology.

3 Rationale/Significance

3.1 Problem Statement

GI functional recovery after surgery is unpredictable and contributes to increased length of stay and postoperative readmissions for ileus.

3.2 Purpose of Study/Potential Impact

The purpose of the Phase 1 study is to determine if the myoelectrical measurements made by the G-Tech Wireless Patch System correlate with clinical markers of postoperative recovery such as passage of flatus/bowel movement, oral tolerance of diet and discharge readiness. Subsequently the data will be studied to establish which information in the signals is important in determining when to feed patients and possibly discharge them.

These pilot prospective, open clinical studies suggests that myoelectrical activity, measured on the abdominal surface with a noninvasive wireless patch system, carries predictive value in determining time to feeding and time to flatus following open abdominal surgery. Having such information in advance of clinical measures could facilitate timely interventions, be it early feeding or delaying feeding as dictated by the patient's unique recovery profile. The G-Tech Wireless Patch System would provide a unique insight into the process allowing for a tailored protocol that could improve patient satisfaction and optimize recovery. The system could also enable feedback on the impact to the overall gastrointestinal myoelectrical activity of medications, particularly opioids, used for pain management that are known to inhibit gastrointestinal function by disrupting the normal recovery patterns of colonic motility.²³⁻²⁵ While it remains to be seen, in addition to predicting time to flatus/bowel movement early on, the ability to continue monitoring the patient may allow one to predict onset of secondary complications, such as wound infections or anastomotic leaks, that are associated with ileus. Although not part of this protocol, given the wireless noninvasive nature of the system the patients could be discharged home with the patches, whereby they would serve as a remote monitoring tool. This could be particularly useful in cases where the patients may have been discharged early and may be at a high risk for readmission. The system would then send updates/alerts to the care team for management and potentially avoid preventable readmissions.

3.2.1 Potential Risks

The risks associated with the G-Tech Patch System are related with the use of the G-Tech Patch (electrical risks, skin allergy or chemical) and the export of the data (anonymized data sent to G tech).

3.2.2 Potential Benefits

There are no direct benefits to participants. The information gained from their experience with the device may decrease healthcare utilization needs of future patients.

4 Study Objectives

4.1 Hypothesis

Myoelectric signaling patterns of the abdominal cavity after surgery will correlate with first flatus.

4.2 Primary Objective

To measure myoelectric signals with the G-Tech WPS and determine if a correlation exists between signal strength and the rate of gastrointestinal recovery following colorectal surgery. Determine the relationship between gastrointestinal myoelectrical signal strength and clinical markers of recovery such as passage of flatus/bowel movement, oral tolerance of diet, and discharge readiness.

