5.2 Outcome Variables

5.2.1 Primary Outcome Variables

GI functional recovery after surgery as measured by first flatus

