6.4.3 Planned Analysis

6.4.3.1 Primary Analyses

The primary endpoint is to determine if there is a correlation between the measured motor activity metrics of the various GI organs with measures of recovery, and to mathematically characterize the correlation in a manner that leads to predictive ability. The study is retrospective without intention to treat. Data analysis is performed by the staff of G-Tech Medical located in Mountain View, CA using proprietary software developed specifically for this purpose. Data is accessed on a secure cloud server to which it was uploaded by the mobile app connected to the patches.

Data analysis consists of extracting the myoelectric motor activity measured by the patches in ten-minute time segments and assigning them to an organ or organs. The motor activity at any one time (instantaneous) and the cumulative activity up to that point in time will be examined for correlation to parameters associated with recovery rate such as time to first flatus, time to first solid meal, time to discharge, etc. This will be done across all time points to find the earliest time that offers predictive value. The specific final analysis approach taken will depend on the findings of this pilot study.

In the study² with colonic myoelectric activity measurements after open abdominal surgery an inverse correlation was found between cumulative colon signal strength and time to first flatus which was approximately linear and was best characterized by the root mean square (RMS) deviation of the residuals from a linear fit, in units of hours. The optimal time for this analysis was found to be at 36 hours after surgery.

Similarly in the study¹ with patients undergoing pancreaticoduodenectomy procedure, a correlation was found between cumulative signal strength of the stomach and time to first full meal that was also inverse but not well represented by a linear or other fit. In this case the analysis involved assigning patients to one of two groups, early and late feeders. The stomach activity data were then tested for predictive value against these groups. Patients with stronger signals were more likely to be in the early feeding group and vice versa. A statistical analysis was performed using a receiver-operator characteristic approach that led

pancreaticoduodenectomy for diet “readiness”. American Journal of Physiology-Gastrointestinal and Liver Physiology, 315(5), pp.G743-G751.

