7.5 Data Collection

Screening, Demographics, and Eligibility Case Report REDCap Form

The Principal Investigator will ensure collection of screening and eligibility data that allows for documentation to show the study subject meets all eligibility criteria and has been properly selected to participate in the study. This can be achieved through a case report form submitted via REDCap. Additionally, demographics and clinical history shall be used to further document the subject's appropriateness for this study and collect the characteristics of the subject that contribute to the analysis of the statistical characteristics of the study population.

Recording Procedure and Clinical Markers Case Report Form

The Principal Investigator will ensure collection of the time of device placement, and the device serial number. The information shall be updated if a new device is used. The Principal Investigator will ensure collection of clinical markers of recovery which at a minimum include time of first flatus, time of first bowel movement, time of first solid meal and time of discharge. These minimum set of inputs should be entered in the G-Tech Patch Monitor App.

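### Oral tolerance and discharge readiness are named in the primary objective but neither defined nor recorded; first solid meal and actual discharge are analysed in their place

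*Combined protocol and SAP*

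**What the plan says.** Section 4.2 sets out to relate myoelectric signal strength to "clinical markers of recovery such as passage of flatus/bowel movement, oral tolerance of diet, and discharge readiness". The synopsis repeats this, and section 3.2 gives the same markers as the purpose of the study. No section defines the last two of these, "oral tolerance of diet, and discharge readiness", and neither is listed as an outcome in 5.2.1 or 5.2.2.

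The minimum data required by section 7.5 are "time of first flatus, time of first bowel movement, time of first solid meal and time of discharge". The primary analysis in 6.4.3.1 gives as its examples "time to first flatus, time to first solid meal, time to discharge". Appendix 3 has a date for first solid food, no field for discharge, and no field for whether the meal was tolerated.

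The background in 2.2 describes the diet marker differently, as "the ability to tolerate solid food without significant nausea and vomiting". It reports that enhanced-recovery programmes feed before the clinical markers appear, that this fails in as many as 25% of cases, and that "it does not work in cases where patients are not ready for it".

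The hypothesis in 4.1 and the primary outcome in 5.2.1 concern first flatus only: "GI functional recovery after surgery as measured by first flatus".

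**The concern.** On the protocol's own account, a first solid meal is a feeding event and tolerance is a recovery event, and early feeding can put the first well ahead of the second. The plan analyses the first under the name of the second. A patient fed early who then vomits, or is put back to nothing by mouth, keeps the early meal time, and nothing in 6.4.3.1 changes it.

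These are slow recoverers, the patients the device is meant to identify. If they carry early times, the association between signal and the diet marker is weakened and partly reflects ward feeding practice. Section 3.2 intends to use the data to learn which signal features show when to feed and possibly discharge patients, so these two markers bear directly on the intended use.

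The discharge half is simpler. No readiness criteria are recorded, so time of discharge supports a statement about discharge and nothing about readiness.

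**Working it through.** **1. Marker against data**

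| Marker in 4.2 | Meaning given | What is recorded (7.5, Appendix 3) | What is analysed (6.4.3.1) |
|---|---|---|---|
| Flatus / bowel movement | The event itself | First flatus, first bowel movement | Time to first flatus; bowel movement under 6.4.3.2 |
| Oral tolerance | 2.2: solid food without significant nausea or vomiting | First solid meal | Time to first solid meal |
| Discharge readiness | None | Time of discharge (7.5 only) | Time to discharge |

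The first row matches. The other two do not.

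**2. Can existing data repair the diet marker?** The only intolerance signal is the clinical ileus item on Appendix 3. It is a single yes/no covering emesis after postoperative day 2, absence of flatus, reversal of the diet order and possible tube placement. It has no date, so it can flag some failed meals but cannot supply a later tolerance time. Section 6.4.3.1 does not link it to meal time.

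**3. The background figure.** Section 2.2 reports tube reinsertion in 128 of 513 patients, printed as 24.7%. 128/513 = 24.95%, and 0.247 × 513 = 126.7. The difference is immaterial: 0.247 × 200 = 49.4 and 0.2495 × 200 = 49.9. Reading this as about 50 of 200 failed first meals here is an assumption.

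**4. Size, as illustration only.** The documents give no correlation, feeding time or failure rate for this study. Assumed: true r = -0.60 between signal and tolerance time T; T with mean 48 h, SD 24 h; a fraction p have T replaced by an early meal time with mean m, SD s; everyone else's meal time equals T. If failure depends only on T or is random, observed r = r_true × corr(T, meal time).

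- *Random failure*, p = 0.247, m = 24, s = 8. Covariance with the standardised signal = 0.753 × (-0.60 × 24) = -10.84. Variance = 0.753 × 576 + 0.247 × 64 + 0.247 × 0.753 × 24² = 433.7 + 15.8 + 107.1 = 556.7, SD 23.59. Observed r = -10.84/23.59 = **-0.46**.
- *Slowest 24.7% all fail*, same meal times. Work in units of (hours - 48)/24. The cut is k = 0.684, with normal density 0.3157. Covariance of T with meal time = (0.753 - 0.684 × 0.3157) - 0.3157 = 0.2214. Mean = -0.3157 - 0.247 = -0.5627. Mean square = 0.5371 + 0.247 × (1 + 1/9) = 0.8115. Variance = 0.8115 - 0.3166 = 0.4949, SD 0.7035. Observed r = -0.60 × 0.2214/0.7035 = **-0.19**.
- *Mild case*, 10% random, m = 48, s = 12. Covariance = 0.9 × (-14.4) = -12.96. Variance = 0.9 × 576 + 0.1 × 144 = 532.8, SD 23.08. Observed r = **-0.56**.

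Other scenarios, by simulation:

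| Failed | Who fails | Early meal mean (SD), h | Observed r |
|---|---|---|---|
| 24.7% | Risk rises with slowness (logistic slope 0.5 to 2 per SD) | 24 (8) | -0.41 to -0.29 |
| 24.7% | Slowest | 36 (12) | -0.33 |
| 24.7% | Random | 36 (12) | -0.49 |
| 24.7% | Slowest | 48 (8) | -0.47 |
| 10% | Slowest | 24 (8) | -0.36 |
| 10% | Random | 24 (8) | -0.54 |

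Under random failure some replaced times fall after T. Capping them at T would bring r slightly nearer -0.60.

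**5. Power.** Using the Fisher z approximation, N = 200, two-sided 0.05, and c for the correlation of surrogate with true marker (assumed): true |r| = 0.3 gives power 0.99, 0.97, 0.85 and 0.56 at c = 1, 0.9, 0.7 and 0.5. True |r| = 0.5 gives about 0.95 even at c = 0.5. Loss of power is serious only for a weak true correlation and a poor surrogate.

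**The case against.** The case against giving this much weight is substantial, and several parts of it stand.

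- **The primary result is untouched.** A reader might infer that the primary objective consists of these two markers, or that the main result is biased. The documents do not support that. Section 4.2 opens with rate of recovery and gives the markers as examples, flatus and bowel movement first. The hypothesis is "Myoelectric signaling patterns of the abdominal cavity after surgery will correlate with first flatus", and first flatus is collected directly.
- **The plan does not say meals merely offered are logged.** Sections 6.1.2 and 7.5 say first solid meal, and Appendix 3 says first solid food. Whether that means served, eaten or kept down is undefined.
- **The background does not separate discharge from recovery.** Section 2.2 makes its early-feeding argument about food and links these programmes to shorter stay. The remark in 3.2 about early discharge and readmission risk concerns home monitoring outside this protocol. The discharge point rests only on the absence of readiness criteria.
- **Failed patients are not lost altogether.** Inpatient ileus is an outcome in 5.2.2 and is correlated with the signal under 6.4.3.2, so many would be flagged there. That does not correct their time on the diet marker.
- **The 24.7% is not a first-meal failure rate.** It is tube reinsertion in another cohort, at postoperative day 3.9 ± 2.9, and some of those patients may have tolerated a first meal.

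This is also a feasibility study that leaves its final analysis open. That argues for modest weight. It does not supply a definition of tolerance, and dates not collected during the stay may be hard to recover later.

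**Conclusion.** The concern holds for two non-primary markers. Oral tolerance and discharge readiness are stated aims with no definition and no data field, and the diet stand-in is one that section 2.2 itself shows can precede recovery. Conclusions about tolerance or readiness would not be supported by the planned data; conclusions about first flatus would be.

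The size cannot be fixed from the documents. With true r, tolerance times, meal times and a 10% to 25% failure rate all assumed, a correlation of -0.60 is observed at between about -0.19 and -0.56. The lower figure is a worst case: it needs every one of the slowest quarter to be fed at about 24 h while every other meal time equals tolerance time. Attenuation appears in every scenario examined. At N = 200 the main harm is to interpretation, with power a secondary issue. The change is worth making, but the study does not stand or fall on it.

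**What to change.** 1. In 6.4.3.1, count a first solid meal as oral tolerance only if it is not followed, within a window fixed in advance, by emesis or reversal of the diet order. Otherwise use the first later solid meal that is not reversed, or censor at discharge.
2. Analyse this endpoint with a rank or time-to-event method that handles censoring; the linear-fit and ROC precedents cited in 6.4.3.1 do not. State that a patient without tolerance by discharge is censored, so that the rule in 6.4.5 of dropping patients with missing data does not remove the slowest ones.
3. Add to Appendix 3 the date of any emesis or diet reversal and the date of the later meal. The ileus item cannot serve, being undated and counting emesis only after postoperative day 2. This is for measurement only, with no change to feeding practice.
4. Report first solid meal separately as a measure of feeding practice.
5. Label the discharge result as time to discharge and draw no conclusion on readiness.

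At minimum, restrict 4.2, the synopsis and the conclusions to first solid meal and time to discharge.

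The cost is two or so added date fields, a few sentences in 6.4.3.1 and some censored tolerance times. Because Appendix 3 is held in REDCap and the signal analysis is done by the manufacturer (7.6 to 7.8), the tolerance time must also be passed across or linked at the site.
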